01.0	17.03.2013	[name] [name] [name]	Original document (includes appendix 01)
0.20	07.05.2013	[name], [name], [name] [name], [name]	Added Appendix 02: Developmental outcomes at age 18 months (prepared by [name]) and Appendix 03: Breast milk intakes (prepared by [name])
03.0	24.05.2013	[name], [name], [name] [name]	Added Appendix 04: The effect of LNS on physical activity (prepared by [name])
04.0	26.07.2013	[name], [name], [name] [name]	Added Appendix 05: Effect on infant and young child feeding practices (prepared by [name])
05.0	25.04.2014	[name], [name], [name] [name]	Main growth SAP: Edited the way SAE's are claculated and presented. Removed adjustment for time in the study and presenting total number of cases per group. Added Appendix 6: Hypothetical Willingness-to- Pay for LNS and Likuni Phala at Baseline (Prepared by [name])
06.0	28.04.2014	[name], [name], [name] [name]	Revised Appendix 05 into version 2.0: Effect on infant and young child feeding practices (prepared by [name])
07.0	28.05.2014	[name], [name], [name] [name]	Added Appendix 7: Long-term acceptability of LNS (lipid-based nutrient supplements) for infants in Malawi (Prepared by [name]) Added Appendix 8: The effect of Lipid-based

J	[name]	Nutrient Supplement (LNS) provision on child
E	[name]	morbidity (Prepared by [name])

2 Introduction

Poor growth and severe childhood stunting are very common in rural Malawi and elsewhere in Sub-Sahara Africa, with known negative consequences for child development and long-term individual and household welfare. To date, few interventions have proven successful in promoting linear growth in early childhood. Preliminary results from Malawi and Ghana suggest that a 6-12 month-long daily complementary feeding of infants with 20-50 g of an energy-dense and highly micronutrient fortified Lipid-based Nutrient Supplement (LNS) may markedly reduce the incidence of severe stunting before the age of 18 months.

The iLiNS-DOSE trial was designed to study the impact of a 12-month LNS provision to infants and young children on their growth, nutritional status and a number of other health outcomes. For this purpose, a total of 1932 infants were enrolled in rural Malawi, randomized to receive for 12 months either no supplement or one of five alternative LNS-preparations (six study groups in total), and intensely monitored for 12-months for a large number of outcomes. Key details of the trial have been recorded at the clinical trial registry at the National Institutes of Health (USA) (www.clinicaltrials.gov), under the registration number NCT00945698. A full trial protocol is available from the contact person to this document.

This document (called "the statistical analysis plan" or SAP) describes the study group's plan for data analysis, management, and storage. The SAP is designed to be evolving over time. Version 1.0 documents the details of the hypothesis testing and other analyses on primary and selected secondary outcomes. Subsequent versions of the SAP will give further details on the analyses and hypothesis testing of additional secondary outcome variables and exploratory analyses from the data.

3 Study objectives

The main aim of the trial is to assess the safety and impact of LNS supplementation on linear growth of infants and young children and to identify individual, household, and village-level characteristics that would modify the effects of LNS on child growth. A secondary aim is to similarly study the impact of LNS on various other (secondary) outcomes in the same target group. Finally, the trial aims to provide descriptive information on issues that might be necessary to facilitate future demand creation for LNS interventions.

The above aims have been broken down into the following first five objectives that were predefined in the trial protocol. The safety aim was not explicitly stated among the predefined objectives in the trial protocol, but was listed under the primary outcomes for analysis.

- 1. To determine the lowest daily dose of LNS that will promote linear growth among 6-18 months old infants in a rural Malawian community with poor food security. *This covers also the objective to study if ANY dose of LNS promotes linear growth among the target group.*
- 2. To assess if LNS made without milk has a linear growth-promoting effect comparable to that of milk-containing LNS (in the above described environment, with 20 and 40 g/day ration sizes).
- 3. To determine the impact of five different LNS supplementation schemes on child dietary intake, morbidity, appetite, micronutrient status, immune function, and neuro-behavioral development.
- 4. To collect information to facilitate future demand creation for LNS interventions, such as end-user knowledge, attitudes and practices related to LNS and other feeding and parental care-giving practices.
- 5. To assess the extent to which household food insecurity and other individual, household, and village-level characteristics modify the effects of LNS on child outcomes.
- 6. To determine if any of the LNS supplements lead to increased risk of serious adverse events.

4 General approach to data analysis

There will be three categories of data analysis.

- 1. For the main aim (safety and linear growth outcomes), the analyses will be driven by predefined primary study hypotheses (see chapter 4 below). Conclusions on this part of the study will be based on formal hypothesis testing.
- 2. For the secondary aim (other outcomes), the analyses will be driven by similar hypotheses to those used for linear growth. These hypotheses have not been predefined in the trial protocol and hence they do not appear in version 1.0 of this SAP. They will, however, be defined as appendixes in subsequent versions of the SAP. For each hypothesis-driven analysis, the SAP will be updated prior to starting the analysis.
- 3. In addition to the hypothesis-driven questions, there will be a large number of exploratory analyses. In the absence of predefined study hypotheses, these analyses will be considered hypothesis-generating, rather than confirmatory.

5 Hypotheses to be tested

As indicated above, version 1.0 of the SAP describes predefined hypotheses only for the linear growth outcomes, i.e. specific objectives 1 and 2. Further hypotheses will be formulated and documented in subsequent SAP versions before the respective analyses are started.

- Objective 1 / hypothesis 1: The change in mean length-for-age Z-score (LAZ) of infants provided with 10, 20, or 40 g/day of LNS from 6 to 18 months of age will be greater than that of infants who receive no dietary intervention at the same age.
- Objective 2 / hypothesis 2: The change in mean LAZ of infants receiving 20 or 40 g/day of LNS without milk from 6 to 18 months of age will not be lower than that of infants receiving a comparable intervention with milk-containing LNS.

6 Data cleaning and procedures on breaking the intervention code

The study group will adopt the following procedures for data cleaning and breaking the intervention code

- 1. In the first phase, a number of investigators will do preliminary cleaning of the data required to the main analyses (safety and linear growth outcomes). At this point, all investigators are totally blinded to the intervention each participant has been receiving.
- 2. A study statistician ([name]) makes a preliminary database that contains semi-clean data required for the main analyses. The database and summary statistics for each variable are distributed to the principal investigators, the members of the board governing trial implementation and the principal biostatistician for the trial. Once these individuals agree that the data are sufficiently comprehensive and clean, the study statisticians ([name], [name], and [name]) are provided with the database and a code that can be used to group the participants who received the same intervention together i.e. that gives group codes 1, 2, 3, 4, 5, and 6 without indicating the actual intervention each group number relates to.
- 3. The study statisticians review the data and complete preliminary analyses for group comparisons (without knowing the actual interventions). Based on these analyses, the study statisticians make suggestions for the amendment of the SAP (e.g. on the treatment of missing values). The investigators listed under 2) above then agree on a revised version of the SAP, after which the intervention code is broken and the main analyses are completed.
- 4. For secondary outcomes, the analyses will be mostly completed by investigators who are not study statisticians. For each of these analyses, data cleaning will be completed as above. Once the analyst has completed the first round of data cleaning without any knowledge about the group information, s/he will request scrambled group information from the

statisticians. This information will again group the participants who received the same intervention together without indicating the actual intervention each group number relates to. For each analyst, the study statisticians provide a new / different set of scrambled group codes – so that two analysts cannot combine their results during the analysis.

- 4. Before the intervention code is fully broken, mistakes found in the data can be corrected in the database, as long as there is an audit trail that indicates the date of correction, the old and new value, justification for the correction and the identity of the person authorizing the change (this is not necessary for the correction of entry errors). After the code is broken, the data on main outcomes will be "frozen" and data can no longer be corrected in the database. Instead, all corrections (also entry errors) will be reviewed and need to be approved by the responsible investigator and documented before programmed into cumulative syntax-files (do-files, one for each data collection form) that will contain the same information as the audit trail described above. These do-files need to be run to clean the data before any subsequent analyses.
- 5. Data cleaning for other data not used for the main analyses will continue even after breaking the intervention code. For each additional data collection form, the data will be similarly frozen by the time first real analyses will be completed from them (the time can vary form by form). Also for these forms, mistakes found before data freezing will be corrected straight into the database whereas those found after the data freezing will be corrected in separate data-cleaning do files. Both correction methods will contain the audit trail that can be used to track all completed changes.
- 6. Any investigator may raise a suspicion for a correctable mistake in the data. If such a suspicion arises, the investigator who has the responsibility over those particular data (each data collection form has a defined responsible investigator) should be informed and s/he should investigate if a correction is needed. If yes, the data managers in Finland and Malawi will be informed and the change will be made and documented either to the database (before data freezing, this will be done in Malawi), or to a correction do-file (after data freezing, this will be done in Finland).

7 Definition of the primary outcomes

Change in length-for-age Z-score (LAZ):

Length for age will be determined from age, sex, and length information at six months (visit 0) and 18 months (visit 52) of participant age, using the Stata macro developed by the WHO using the WHO 2006 multi-centre growth standard. The values will be rounded to two decimal points. The change (expressed with two decimals) will be calculated by subtracting the value at 6

months from the value at 18 months of age. *The data will be extracted from Form 00: Q2.5; Form 04: Q1.2, Q2.2*

8 Safety outcomes

Incidence of serious adverse events (SAE) during the observation period.

SAE will be defined as an event determined to be an SAE by the study physician. The SAEs will be categorized into five categories: Death, life threatening event, inpatient hospitalization, significant disability or other serious adverse event. *The data will be extracted from Form 29, Q3.2.*

9 Basis for the analysis: Intention to treat and per protocol

Primarily, the analysis will be based on the principle of modified intention-to-treat. The modification concerns six participants who were accidentally allocated to another group than actually randomized. For each participant, the randomization code was pre-packed and sealed in an individual envelope that was opened and used for group allocation at enrolment. For these 6 individuals, the randomizer made a recording error, i.e. s/he noted down in a data collection form an incorrect group code or wrote the code with unclear handwriting. The incorrect code was later transcribed into the computer software that was used to plan participant visits and allocate interventions. These six participants were told to belong to the erroneously recorded intervention group and they received that intervention throughout the trial – hence they will also be analyzed in that group (rather than the one written on the randomization slip).

All randomized participants are eligible to be included in the analyses, with the exception that subjects with missing data on an outcome variable will be excluded for the analysis of that outcome. For variables targeted to be measured every 6-months, the data are considered missing if the actual measurement date is over +/- 8 weeks from target.

Number of participants with non-missing values analyzed for each end point will be presented by treatment groups.

Besides the intention to treat, there will be two per protocol analyses, adjusting for the adherence to the dietary supplementation. In the first per protocol analysis, the statistical model will include a variable that indicates the number of intervention doses delivered to the participant during the time period for which the participant received the study supplements (the supplements were delivered every two weeks). In the second per protocol analysis, the statistical model will include a related variable that indicates the number of days when the participant's guardian indicated that the participant had eaten the study supplement (this information was collected on a daily basis).

10 Time points for the analyses

All the main analyses will primarily cover the period from enrolment (when the participants are 6 months old) to the end of the intervention (when the participants are 18 months old).

Secondarily, there will be a growth analysis after a 2-year post-intervention period, i.e. covering a period from enrolment to when the participants are 42 months old. SAE data will not be collected or analyzed after the participants have turned 18 months old.

11 Presentation of the study findings and hypothesis testing

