12.2 Preparing anthropometric data for analysis

All the anthropometric measurements were completed in triplicate during each study visit. But for the analysis, the team will use the mean of the first two readings if they do not differ more than by a pre-specified tolerance limit. If they do, the third measurement will be compared with the first and second measurements and the pair of measurements that has smaller difference will be used to calculate the mean which will be used in analyses. If there are only one or two repeated measurements mean of those two will be used for the analyses.

The agreed tolerance limits between the first two measurements are:

- 1. length/height ≤ 0.5 cm
- 2. circumferences (head, MUAC) ≤ 0.5 cm
- 3. infant/child weight ≤ 0.1 kg
- 4. adult weight ≤ 0.1 kg
- 5. skinfold thickness $\leq 2.0 \text{ mm}$

The length, circumference and skinfold thickness measurements were recorded to last complete unit (mm). To account for the bias of always rounding the values a bit downwards, half a unit will be added to all length, circumference and skinfold thickness measurements prior to the analysis. This procedure is not done for weight measurements, since they were recorded accurately with electronic scales.

Missing growth values will be treated as missing, i.e. there will be no growth data imputation from the other data. Imputation is considered unreliable due to long time-interval between anthropometric measurements, at an age when growth faltering is common.

When measuring change in anthropometric values between two time intervals, the change will be treated as missing if there is a missing value in either of the respective time points.

12.3 Multiple comparisons

The study involves multiple objectives and therefore multiple sets of hypothesis. Statistically, the different sets of hypotheses are considered independent families of hypotheses. Statistical adjustment for multiple comparisons in one family of hypotheses does not need to consider the other families.

For efficacy analysis, each family consists of 5 hypotheses, each comparing an intervention group versus the control group. The Holm's adjustment method is used.

For safety analysis, it is preferable to err on the cautious side (Nauta, 2010). We began with testing the global null hypothesis of no difference between groups. If the global null hypothesis is rejected, raw P-values are used in the comparisons between intervention and control groups.

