12.6 Covariate adjustment

The final decision on the use of covariates in main analyses will be decided based on preliminary analyses on the final dataset that includes information on the clustering of participants in the same group but does not provide information on the actual intervention delivered to each group.

At this stage, four different regression models for change in LAZ will be constructed, first of these with no covariate adjustments and models 2-4 with various adjustments. If the pointestimates for the regression co-efficient for the intervention group differ in any of the models by more than 10% from that in the unadjusted analyses, the adjusted analysis will be primarily presented in the eventual publications. If all the differences are smaller than 10% (Maldonado & Greenland, 1993), the results in the tables will be shown without covariate adjustments, but model 4 results will be provided in the text as supplementary information.

The four models include:

- 1. No covariate adjustment
- 2. Adjustment for baseline LAZ-score
- 3. Adjustment for baseline WHZ-score
- 4. Adjustment for baseline LAZ-score and baseline WHZ-score and for any of the variables presented in tables 1a and 1b showing statistically significant association (at p<0.1 level) with the change in LAZ-score

13 Storage and release of data

The data meta-data will be stored in a tailor-made hierarchical database, consisting of a MS Access front-end and MySQL tables in the back-end. The database, associated metadata, and form –specific do-files that contain all cumulative data corrections for the respective data collection forms are stored at a computer server at the University of Tampere and daily copied to

a server at the Mangochi research site, University of Malawi. A study statistician ([name]) acts as the manager for these data.

When an investigator wishes to perform certain analyses, s/he will request the respective data from the above-indicated data manager. The data manager will export all the data from the respective data collection form into an excel or Stata file, run the cumulative data correction do-file and then provide the corrected data, together with the syntax for the correction do file (that documents all the completed data editions) to the person requesting the data.

The databases and the do-files will be named with systematic naming format and stored at the central server at the University of Tampere. For each article, the following files will be stored:

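### Section 6 allows SAP amendments of unlimited scope after the six coded groups have been compared, which could lift the family-wise error modestly above 5%

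*SAP*

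**What the plan says.** Section 6, step 2, gives the study statisticians the database and a code that "gives group codes 1, 2, 3, 4, 5, and 6 without indicating the actual intervention each group number relates to". In step 3, "The study statisticians review the data and complete preliminary analyses for group comparisons (without knowing the actual interventions"). The next sentence makes those comparisons the basis for changing the plan: "Based on these analyses, the study statisticians make suggestions for the amendment of the SAP (e.g. on the treatment of missing values"). The listed investigators "then agree on a revised version of the SAP, after which the intervention code is broken and the main analyses are completed".

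Section 12.6 works at the same stage: "The final decision on the use of covariates in main analyses will be decided based on preliminary analyses on the final dataset", a dataset that carries the coded grouping. There, "four different regression models for change in LAZ will be constructed, first of these with no covariate adjustments and models 2-4 with various adjustments". Adjusted results become the main presentation if the intervention coefficients "differ in any of the models by more than 10% from that in the unadjusted analyses". The section does not say which of models 2 to 4 is then the adjusted analysis.

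The missing-data rule that step 3 holds open for amendment is already written in section 12.2: "Missing growth values will be treated as missing, i.e. there will be no growth data imputation from the other data".

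**The concern.** The primary test compares each of five LNS groups with control at a Holm-adjusted 5% level (sections 11.3 and 12.3). That level is exact only if the outcome definition, exclusions and model are fixed without regard to the between-group differences. Here they may be revised after those differences have been computed on the true grouping, and because of what was found.

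Coding prevents deliberate steering towards a named arm. It does not prevent a preference for the rule under which the six groups differ most, or least, because that can be seen without labels. At stake is some loss of error control on the primary comparison. The non-inferiority analysis in section 11.4 is exposed to the same freedom, but its size was not calculated here.

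**Working it through.** The SAP states no error rate for this step, so there is no figure to reproduce. The check has three parts.

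**1. Does hiding the labels remove the information?** No. The F statistic for any difference among six groups is the same however the codes 1 to 6 are shuffled among the arms. Anyone holding the coded data can rank candidate rules by it.

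**2. How much could label-free selection matter?** Null simulation, with these inputs:

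- From the SAP: 1932 infants in six groups (section 2); five comparisons with control, Holm at 0.05 (sections 11.3 and 12.3); four candidate models (section 12.6).
- Assumed: equal groups, 1932 / 6 = 322 each; no true difference between arms; model 4 taken as baseline LAZ, baseline WHZ and three further covariates, each correlated 0.1 with the outcome; the correlations of LAZ change with baseline LAZ and WHZ shown in the table.
- Selection rule: take the model with the largest six-group F.
- Family-wise error: share of runs with at least one Holm rejection, that is, smallest raw p below 0.05 / 5 = 0.01. The p-values come from a regression with variance pooled over all six groups, a close stand-in for the two-sample t-tests.
- 4000 runs per row.

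| r with baseline LAZ | r with baseline WHZ | Unadjusted model fixed in advance | Largest F of four models | Difference |
|---|---|---|---|---|
| -0.20 | 0.10 | 4.1% | 5.6% | 1.5 points |
| -0.30 | 0.20 | 4.6% | 6.6% | 2.0 points |
| -0.45 | 0.25 | 4.7% | 7.9% | 3.2 points |

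Monte Carlo standard error, middle row: sqrt(0.066 × 0.934 / 4000) = 0.004, or 0.4 points. A separate null check of the same kind gave 5.0% rising to 6.7%.

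If one alternative exclusion rule is also open (10% or 20% of children dropped at random), the selected-rule error is 7.8% to 10.1%. No such rule stands in the SAP, so this only shows what an open amendment clause could add.

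**3. Does the 10% criterion in section 12.6 restrain the choice?** Hardly, when there is no effect. In the null runs at least one of the five coefficients moved by more than 10% of its unadjusted value, in at least one of models 2 to 4, in 99.9% to 100% of runs. The arithmetic explains this. In SD units, the standard error of a difference between two arms is sqrt(2 / 322) = 0.079, so a typical null coefficient is about 0.079 and a tenth of it about 0.008. Chance imbalance in baseline LAZ is also about 0.079 SD. With r = -0.3, adjusting for it typically shifts the coefficient by 0.3 × 0.079 = 0.024, three times the threshold. The criterion would thus almost always call for adjustment, leaving the choice among models 2 to 4 unspecified.

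**The case against.** The plan has real safeguards. The statisticians only suggest; the investigators agree the revised SAP; the code is broken after that; and section 14 requires new versions to be approved, numbered and dated. The main choices are already written: t-tests with Holm, the 8-week window in section 9, no growth imputation, four listed models. Applying a written criterion to coded data is not the same as inventing a rule. The simulation also assumes someone who always takes the largest F, which nobody is said to do. All of this stands, and it is why the size is given as a worst case. It does not close the gap: step 3 sets no limit on what may be amended, and section 12.6 leaves the adjusted model unnamed.

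Two stronger readings are tempting.

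- **That the control arm is easy to spot.** With 270 children per arm and the same true benefit in all five LNS arms, control has the lowest mean in 66% of trials at 0.1 SD and 96% at 0.2 SD. But 270 is not in the SAP, and the equal effect is assumed; objective 1 seeks the lowest effective dose, so a 10 g arm close to control is possible. With no effect, where the 5% level is defined, control is lowest 1 time in 6 (17%). These figures therefore do not show a loss of error control. Supplement-delivery data would reveal the control code if they were in the coded database, but the SAP does not say that they are.
- **That rules were in fact chosen to favour a result.** The version log attributes no change to the coded review, and its only stated later edit to the main growth plan concerns presentation of serious adverse events. Section 2 of Appendix 7 reports no statistically significant growth effect, which limits the consequence for the superiority claim.

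**Conclusion.** The point holds as a weakness of procedure. Amendments of open scope may follow, and rest on, comparisons of the true groups, and covariate adjustment is decided at the same stage on the treatment coefficients themselves. This is weaker than unblinded selection, and no misuse is shown.

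The plausible cost is modest: family-wise error of about 6% to 8% instead of the Holm 5%, over the four listed models. That rests on equal groups of 322, correlations not given in the SAP, and selection always by the largest F. Less determined selection would cost less. It merits correction because a sequence without the problem is available at little cost.

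**What to change.** 1. Settle missing-data and exclusion rules on data pooled over arms, or with group codes randomly permuted across participants so that they carry no true grouping.
2. Replace the 10% change-in-coefficient rule in section 12.6 with a covariate set named in advance, for example baseline LAZ and WHZ, and name the one model that is primary. The 10% rule cannot run on pooled data, so changing the order of steps is not enough.
3. Sign the SAP, and only then release the true coded grouping.
4. Log any later change with its reason and report it beside the rule it replaces, as a sensitivity analysis. If the coded review has already taken place, list every rule changed after it in the same way, or state that there were none.

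The cost is a rewrite of section 12.6 and of section 6, step 3, and the loss of a data-driven choice of covariates. No further data are needed.
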